6.1. General Methods

Statistical methodology and analyses are in accordance with the principles outlined by the ICH E9 guidelines. All statistical analyses will be conducted using SAS statistical software version 9.4 or above.

Tables, listings and figures (TLFs) will be produced in accordance with the principles outlined by the ICH E3 guidelines.

Data summaries will use descriptive statistics (number of patients [n], mean, standard deviation [SD], standard error [SE], median, minimum, and maximum) for continuous variables, and frequency and percentage of patients for categorical and ordinal variables, unless otherwise specified. For continuous variables, if $n < 5$ then only median, min and max will be presented.

Unless otherwise specified, all statistical tests will be two-tailed using a 0.05 level of significance. All confidence intervals (CIs) will be two sided 95% CIs.

Only visits mapped to scheduled visits will be included in by-visit summaries. All visit assessment data will be included in shift tables and will appear in the patient listings.

In general, endpoints assessed in Parts I and III will be summarized for Parts I and III combined and endpoints assessed in Part II will be summarized separately for Part II.

For assessments conducted at each visit, analyses for Parts I and III combined will include Week 28 assessment, but Week 30 assessment will not be included. Summary for Part II will include Week 28 (the randomized withdrawal baseline) and Week 30.

For analyses performed by time period, the date of Week 28 and Week 30 will be considered as the first and last day of Part II, respectively. Summary for Parts I and III combined will not include period between Week 28 assessment and Week 30 assessment, which will be covered under Part II summary.

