	Day after Part II first dose (or Date of randomization, if first dose date is missing) - Week 30 visit date (or Day 224 if subject terminated before Week 30 visit)	Day 210	Week 30
	Day 225 - 262	Day 238	Week 34/Part III
	Day 263 - 332	Day 287	Week 41
	Day 333 - 382	Day 378	Week 54
	≥Day 383	Day 385	Week 55
Vital sign, Weight, Height	Day 2 - 21	Day 14	Week 2
	Day 22 - 35	Day 28	Week 4
	Day 36 - 49	Day 42	Week 6
	Day 50 - 80	Day 56	Week 8
	Day 81 - 150	Day 105	Week 15
	Day 151 – Date of first dose of double-blind IMP (or Date of randomization, if first dose date is missing) if patient is randomized; Day 151 – Day 203 if	Day 196	Week 28/Beginning of Part II

This document is confidential.

Statistical Analysis Plan for Interventional Studies

Sponsor: Teva Branded Pharmaceutical Products R&D, Inc./Nuvelution TS Pharma, INC.
 Protocol No.: TV50717-CNS-30047

Assessment	Study Day Window	Scheduled day	Scheduled Visit/Week
	patient is not randomized		
	Day after Part II first dose (or Date of randomization, if first dose date is missing) - Week 30 visit date (or Day 217 if subject terminated before Week 30 visit)	Day 210	Week 30
	Day 218 - Day 231	Day 224	Week 32
	Day 232 - 262	Day 238	Week 34/Part III
	Day 263 - 332	Day 287	Week 41
	Day 333 - 382	Day 378	Week 54
	≥Day 383	Day 385	Week 55
ECG	Day 2 - 42	Day 28	Week 4
	Day 43 - 126	Day 56	Week 8
	Day 127 - 287	Day 196	Week 28
	≥ Day 288	Day 378	Week 54
Chemistry/ Hematology/ Urinalysis	Day 2 - 126	Day 56	Week 8
	Day 127 - 287	Day 196	Week 28
	≥ Day 288	Day 378	Week 54

After mapping the data to the analysis visits of unscheduled and early termination visits, the following rules will apply unless other handling is specified for a particular analysis.

- If there is a scheduled visit in the analysis window, the scheduled visit will be selected.
- If there is no scheduled visit, but an early termination visit, the early termination visit will be selected.
- If there are no scheduled or early termination visits, the record closest to the planned assessment day will be selected for analysis.
- If there are no scheduled or early termination visits, and 2 records are equidistant from the scheduled day, then the later record will be selected.
- If a patient has no scheduled record or early termination/unscheduled visits in an analysis window, the patient will be considered missing at that visit.

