9.13. Columbia-Suicide Severity Rating Scale (C-SSRS)

The C-SSRS children's since last visit (SLV) scale is administered per [Table 3](#). Patients will be placed into categories for suicidal ideation and for suicidal behavior based on their responses to various questions.

The suicidal ideation categories will be determined as follows by examining the response to the 5 questions under Suicidal Ideation.

This document is confidential.

Statistical Analysis Plan for Interventional Studies

Sponsor: Teva Branded Pharmaceutical Products R&D, Inc./Nuvelution TS Pharma, INC.
 Protocol No.: TV50717-CNS-30047

Type	Section
Suicidal ideation	
(0) None – if response is No to Questions 1 and 2
 
(1) Wish to be Dead – if response to Question 1 is Yes and responses to Questions 2-5 are No.
 
(2) Non-Specific Active Suicidal Thoughts – if response to Question 2 is Yes and response to Questions 3-5 are No.
 
(3) Active Suicidal Ideation with Any Methods (Not Plan) without Intent to Act – if response to question 3 is Yes and response to questions 4 and 5 are No.
 
(4) Active Suicidal Ideation with Some Intent to Act, without Specific Plan – if response to Question 4 is Yes and response to Question 5 is No.
 
(5) Active Suicidal Ideation with Specific Plan and Intent – if response to Question 5 is Yes.

For suicidal behavior, the following categories will be used. The categories will be determined based on the response to the questions under suicidal behavior.

Type	Section
Suicidal behavior	
(6) Preparatory Acts or Behavior – if response to Preparatory Acts and Behavior is Yes and responses to Actual Attempt, Interrupted Attempt, Aborted Attempt, and Completed Suicide are No
 
(7) Aborted Attempt – if response to Aborted Attempt is Yes and responses to Actual Attempt, Aborted Attempt, and Completed Suicide are No.
 
(8) Interrupted Attempt – if response to Interrupted Attempt is Yes and response to Aborted Attempt, and Completed Suicide are No.
 
(9) Actual Attempt – if response to Actual Attempt is Yes and Completed Suicide is No.
 
(10) Completed Suicide - if response to Completed Suicide is Yes
 
(0) None – if responses to all the above 4 questions are No.

Suicidal ideation or behavior will be derived as the highest suicidal ideation or behavior score at the visit. Score of 0 represent “No Suicidal Ideation/Behavior”.

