The frequency and percentage of suicidal ideation, suicidal behavior, suicidal ideation or behavior, and self-injurious behavior without suicidal intent from SLV version will be summarized by visit. Separate summaries will be prepared for the Parts I and III combined for all patients based on the Safety Analysis Set, and Part II by treatment group for the RWSAF Population.

Frequency and severity of suicidal ideation or behavior will also be summarized, using a shift table to examine changes in above C-SSRS scores from baseline compared to the worst (highest) category in the Parts I and III combined and Week 28 to Week 30 visit for Part II.

This document is confidential.

10. Interim Analyses

One interim analysis for Part I data is planned after 100 patients completed Part I. No blinded data from Part II will be included in the interim analysis, and hence, no alpha adjustment is needed for the analysis of the key efficacy endpoint in Part II.

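### The window rule drops unscheduled since-last-visit C-SSRS records from the by-visit tables, and records between the Week 30 visit and Day 225 fall in no window

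*SAP*

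**What the plan says.** SAP Section 6.4 assigns unscheduled and early-termination records to windows for by-visit analyses and then selects one record per window. The first selection rule is "If there is a scheduled visit in the analysis window, the scheduled visit will be selected". Failing that, an early-termination record is taken, and failing that the record nearest the planned day. These are defaults: "the following rules will apply unless other handling is specified for a particular analysis".

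Section 9.13 opens with "The C-SSRS children's since last visit (SLV) scale is administered per" Table 3. In the continuation of Table 3, the unscheduled-visit column marks this scale as done at the investigator's discretion. Section 9.13 then says that the frequencies for ideation, for behavior and for "self-injurious behavior without suicidal intent from SLV version will be summarized by visit". This is done once for Parts I and III combined and once for Part II by treatment group. The scoring sentence is "Suicidal ideation or behavior will be derived as the highest suicidal ideation or behavior score at the visit".

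On shifts, Section 9.13 compares baseline with the "worst (highest) category in the Parts I and III combined and Week 28 to Week 30 visit for Part II". Section 6.1 adds: "All visit assessment data will be included in shift tables and will appear in the patient listings".

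The C-SSRS shares its window row in Section 6.4 with the CDI-2. The Week 30 window closes at the Week 30 visit for patients who attend it, and at Day 224 for those who terminated before it. The Week 34 window runs from Day 225 to Day 262. The YGTSS Week 34 window instead opens the day after the Week 30 visit.

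**The concern.** For a point-in-time measure such as blood pressure, preferring the scheduled record costs one reading among several of the same thing. A since-last-visit scale differs, because each interview reports on the interval since the one before. Two records in one window then describe different days, and dropping one drops what was reported for those days. The next interview need not report it again.

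Unscheduled interviews are discretionary and are plausibly prompted by clinical concern, so the dropped records may be positive more often than the kept ones. Safety is the primary objective (Section 3.1), and Section 4.1 names the C-SSRS as a safety endpoint for Parts I and III and for Part II. At stake is whether the by-visit suicidality tables show what was recorded.

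**Working it through.** No figure in the plan bears on this point, so the check applies the Section 6.4 rules to a patient on the nominal Table 3 schedule.

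**Inputs.** Scheduled post-baseline C-SSRS: Days 14, 28, 56, 105, 196, 210, 238, 287, 378 and 385 (Table 3). Windows from Section 6.4: 2–21, 22–42, 43–80, 81–150, 151 to first blinded dose, the next day to the Week 30 visit, 225–262, 263–332, 333–382, and 383 onward. Assumed: Week 28 visit on Day 196, first blinded dose on Day 197 (Table 3, footnote p of the continuation), Week 30 visit on Day 210, and every scheduled C-SSRS done.

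**Step 1: where an unscheduled record goes.** Days 2 to 385 are 384 days. Less 10 scheduled days, 374 remain.
- Days 211 to 224 lie in no window: 224 − 210 = 14 days.
- The other 374 − 14 = 360 days lie in a window that holds a scheduled record. An unscheduled C-SSRS on any of them is displaced from the by-visit table.

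With the ±3-day allowance, the Week 30 visit falls on Days 207 to 213, so the gap runs from 224 − 213 = 11 to 224 − 207 = 17 days.

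**Step 2: does Section 9.13 override the default?** Its scoring sentence takes the highest score at the visit, which ranks answers within one interview and not records across a window. Its worst-category wording belongs to the shift table. Nothing else is said for the by-visit tables, so the default applies.

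**Step 3: early termination.** A patient with a Week 15 visit on Day 105 who terminates on Day 140 has both records in Days 81–150, and the scheduled one is kept. A patient who attends Week 30 and terminates on Day 217 has an early-termination C-SSRS in no window. A patient who terminates during Part II before Week 30 is not affected by the first rule, since no scheduled Week 30 record exists.

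**Step 4: illustration in Part II.** Suppose an unscheduled interview on Day 203 gives ideation category 4 and the Week 30 interview on Day 210 gives 0. The by-visit table by treatment shows 0. The shift table depends on the reading. Taking the Week 30 record alone gives 0 to 0 (if Week 28 was 0). Taking all visit data, as Section 6.1 says, gives 0 to 4.

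**Step 5: days not represented.** If recall restarts at each interview, the share of the interval carried only by the dropped record is (unscheduled day − previous scheduled day) / (scheduled day − previous scheduled day):
- Part II, Day 203: (203 − 196)/(210 − 196) = 7/14 = 50%. Across Days 198 to 209 it runs from 2/14 = 14% to 13/14 = 93%.
- Week 28 window, Day 180: (180 − 105)/(196 − 105) = 75/91 = 82%.
- Week 54 window, Day 350: (350 − 287)/(378 − 287) = 63/91 = 69%.

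The days are chosen for illustration. The shares are calendar time, not event rates or bias.

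**The case against.** The strongest reply is that the selection rules serve by-visit analyses only, and that the record reaches the report by other routes. Section 6.1 sends all visit data to the shift tables and listings. Section 9.13 uses the worst category for Parts I and III. Section 9.4 includes SMQ tables for suicide and self-injury, prepares all adverse event tables for Part II by treatment received, and does not depend on visit windows. Unscheduled C-SSRS interviews are discretionary and may be few.

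All of that stands, and it rules out several stronger readings:
- **The event disappears from the report.** It does not. It stays in the listings, in the Parts I and III shift and, if reported as an adverse event, in the SMQ tables.
- **It is lost from the Part II shift.** This is not established. Section 6.1 points to inclusion, and the Part II wording in Section 9.13 can mean the Week 30 record or the worst over the interval.
- **The C-SSRS is the only by-arm comparison of suicidality in Part II.** The SMQ tables are another.
- **The patient is never asked about the event again.** That recall restarts at an unscheduled interview is inferred from the name of the scale. The SAP does not say so.

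The reply does not rescue the by-visit tables. Section 9.13 plans them as an endpoint display, and the stated rule leaves recorded findings out of them. The SMQ route works only if the finding was also reported as an adverse event.

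**Conclusion.** The concern holds for the by-visit C-SSRS tables, including the Part II table by treatment. A positive unscheduled record, or an early-termination record whose window already holds a scheduled one, is omitted, and the kept record covers other days. For patients who attend Week 30, records from the next day to Day 224 reach no window at all. For the Part II shift the finding is one of ambiguity: two programmers could follow the text and produce different cells for the same patient.

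The size in patients is unknown, because the SAP does not give the number of unscheduled or early-termination C-SSRS interviews. The counts of 360 and 14 days assume the nominal schedule, and the look-back shares also assume that recall restarts at each interview. These are descriptive safety tables, so no hypothesis test is affected. The correction is still worth making, because it concerns a named safety endpoint in a trial whose primary objective is safety.

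**What to change.** Make three changes:

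1. In Section 9.13, as the other handling that Section 6.4 permits, state that the C-SSRS value for each analysis window is the worst (highest) category over all scheduled, early-termination and unscheduled since-last-visit records in that window. This extends the worst-category principle that Section 9.13 already uses for Parts I and III.
2. In Section 6.4, open the C-SSRS Week 34 window the day after the Week 30 visit for patients who attend it, as the YGTSS row does. Without this, a worst-in-window rule cannot recover Days 211 to 224. The row is shared with the CDI-2, so either move both or split the row.
3. In Section 9.13, state that the Part II shift runs from Week 28 to the worst category over all post-Week 28 Part II records.

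The cost is a few sentences, a maximum-over-window derivation and one changed window boundary. No new data are needed. It should be done before the Part II codes are opened.

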6.5. Pooling of Centers

Patients will not be pooled by centers.

This document is confidential.

7. Demographic, Other Baseline Characteristics and Medication

7.1. Patient Disposition and Withdrawals

Descriptive statistics of frequency and percentage will be presented overall in one column. The ITT Analysis Set will be used as the denominator for calculating percentages.

The following data will be summarized:

- Total patients enrolled (only frequency);
- Patients enrolled but not treated (and the reason);
- Patients in the ITT and Safety Analysis Sets. Only overall will be presented;
- Patients who withdraw from the study (and reason for withdrawing) before randomization (during Part I);
- Patients randomized in Part II;
- Patients who complete the randomized drug withdrawal period (Part II);
- Patients who withdraw from the study (and reason for withdrawing) during randomized drug withdrawal period (during Part II);
- Patients who complete the study;
- Patients who withdraw from the study (and reason for withdrawing) after randomized drug withdrawal period (during Part III).

In addition, Part II disposition will be summarized. Table will include patients in the RWITT, RWSAF, RWmITT, and RRWmITT populations, separately by treatment. Percentages for RWSAF, RWmITT, and RRWmITT will be computed using the number of subject in the RWITT population as denominator. The following data will be summarized:

- Total patients in the RWITT population (only frequency);
- The RWSAF, RWmITT, and RRWmITT populations by treatment;
- Patients who complete the randomized withdrawal period;
- Patients who withdraw from the study (and reason for withdrawing) during the randomized withdrawal period (Part II).

A listing of study completion will be provided for the ITT Analysis Set. A listing for analysis dataset with reason patient is excluded from the analysis set will also be provided for all patients enrolled.

7.2. Demographic and Other Baseline Characteristics

Patient demographics and baseline characteristics will be examined. Summaries for demographics and baseline characteristics will be presented for the ITT and Safety Analysis Sets, and the RWSAF, RWmITT, RRWmITT populations. Unless otherwise specified, for all summaries for ITT and Safety Analysis Sets, 30047 baseline will be used and table will be presented in one overall column, and for all summaries based on the RWSAF, RWmITT, RRWmITT populations, randomized withdrawal baseline will be used and table will be presented by treatment arm.

This document is confidential.

BMI will be computed as:

$$\text{BMI (kg/m}^2\text{)} = \frac{\text{Weight at baseline (kg) for ITT and Safety Analysis Sets (or randomized withdrawal baseline for RWSAF, RWmITT, and RRWmITT populations)}}{(\text{Height at baseline for ITT and Safety Analysis Sets [or randomized withdrawal baseline for RWSAF, RWmITT, and RRWmITT populations] [m]}^2)}$$

In addition, normal age and sex-based z-scores and percentiles for BMI will be determined using the WHO growth charts. Age and sex-based BMI categories includes: Underweight (< 5 percentile), Normal (≥ 5 - < 85 percentile), Overweight (≥ 85 - < 95 percentile), Obese (≥ 95 percentile). Age at baseline for ITT and Safety Analysis Sets (or randomization withdrawal baseline for RWSAF, RWmITT, and RRWmITT populations) will be used.

Variables below will be included in the summary:

- Continuous variables at baseline or randomized withdrawal baseline: patient age, weight, height, body mass index (BMI), BMI World Health Organization (WHO) adjusted z-scores and percentile, time from Tourette syndrome diagnosis to the date of informed consent in current study in years and baseline TTS of YGTSS.
- Categorical variables at baseline or randomized withdrawal baseline: patient sex, race, ethnicity, country, age group (6-11 years; 12 –18 years), weight group (20-<30 kg, 30-<40 kg, or ≥ 40 kg), sex, race, ethnicity, BMI categories.
- Categorical variables at parent baseline: age group (6-11 years or 12 – 16 years), use of a strong CYP2D6 inhibitor (Yes/No), CYP2D6 genotype (Poor CYP2D6 metabolizer/ Non-poor CYP2D6 metabolizer), and CYP2D6 impairment status (Impaired/Not impaired).

Refer to Section 6.2.1 for the definitions of all baselines.

Continuous variables will be summarized using descriptive statistics. Categorical variables will be summarized using frequency and percentage for each category. Missing categories will be presented if necessary.

7.3. Medical History

Medical and psychiatric history, including dates of diagnoses and procedures and whether the condition is ongoing, if applicable, will be collected. Each condition will be recorded as a verbatim term, date of onset, date resolved, and a checkbox that indicates ongoing conditions. For patients from Study TV50717-CNS-30046 and TV50717-CNS-30060, The medical and psychiatric history form from the parent study will be copied over to TV50717-CNS-30047. Adversed events that started in the parent study will also be carried over to TEV50717-CNS-30047 medical history page and summarized as part of medical history.

Psychiatric and medical history will be coded using the Medical Dictionary for Regulatory Activities (MedDRA) Version 20.1.

Medical and surgical history will be summarized for the Safety Analysis Set and the RWSAF population by system organ class (SOC) and MedDRA preferred term (PT). Patient data will be listed.

7.4. Prior Medication and Other Therapies

Any prior medications will be entered manually by the sites from IMP administration in the parent study to follow-up. Medications will be coded according to the WHO Drug Version: June 2017. Preferred drug name, Anatomical/ Therapeutic/ Chemical (ATC) class will be reported for inclusion in the database.

This document is confidential.

Statistical Analysis Plan for Interventional Studies

Sponsor: Teva Branded Pharmaceutical Products R&D, Inc./Nuvelution TS Pharma, INC.
Protocol No.: TV50717-CNS-30047

Medication summaries based on ATC level 3 and the preferred drug names will be produced for the Safety Analysis Set. The summaries will present the frequency and percentage of patients who used any medication in an ATC class, or any medication based on a single preferred drug name. Medication summaries will be sorted by descending total frequency of ATC class and by PT within ATC class. Patients will be counted only once for each medication class and each preferred drug name.

7.4.1. Prior Medication

Prior medications and therapies will include all medications stopped before the first day of study drug administration. Medications stopped during Part I will be considered as prior medications for summary of Part II. Prior medication will be summarized by the ATC level 3 and preferred name for the Safety Analysis Set and the RWSAF population. Same summary will be repeated for prior antidepressant and ADHD medication use. These medications are identified by the ATC codes of:

ADHD medications:

N-NERVOUS SYSTEM

N06-PSYCHOANALEPTICS

N06B-PSYCHOSTIMULANTS, AGENTS USED FOR ADHD AND NOOTROPICS

N06BA-Centrally acting sympathomimetics

N06BC-Xanthine derivatives

N06BX-Other psychostimulants and nootropics.

Antidepressant:

N-NERVOUS SYSTEM

N06-PSYCHOANALEPTICS

N06A-ANTIDEPRESSANTS

N06AA-Non-selective monoamine reuptake inhibitors

N06AB-Selective serotonin reuptake inhibitors

N06AF-Monoamine oxidase inhibitors, non-selective

N06AG-Monoamine oxidase A inhibitors

N06AX-Other antidepressants.

7.4.2. Other Therapies

Prior non-pharmacological treatment will be collected in the CRF. Type of treatment/procedure and indication will be summarized.

Prior pharmacological treatment given for TS will be summarized. Table will include number of patients with previous treatment given for TS, total duration of treatment, and best response to treatment. For an ongoing treatment, date of informed consent will be used to compute duration.

Prior non-pharmacological treatments will be listed.

This document is confidential.

8. Efficacy

All assessments in the Parts I and III combined are exploratory in nature and no inferential statistics will be applied; however, inferential statistics will be applied to the efficacy endpoint in the Part II. In general, all efficacy endpoints will be included in the efficacy analyses for the Parts I and III combined based on ITT Analysis Set. Summary for the Parts I and III combined will include one column for all patients and will not include the assessments during Part II. Efficacy endpoints that are assessed in both Parts I and III and in Part II will be presented in two sets of the tables: one for Parts I and III combined, and one for Part II.

